10.4.3. Collection of Pregnancy Information

Male participants with partners who become pregnant

- Investigator will attempt to collect pregnancy information on any male participant's female partner of a male study participant who becomes pregnant while participating in this study. This applies only to male participants who receive bintrafusp alfa.
- After obtaining the necessary signed informed consent from the pregnant female partner directly, the investigator will record pregnancy information on the appropriate form and submit it to GSK within 24 hours of learning of the partner's pregnancy.
- The female partner will also be followed to determine the outcome of the pregnancy. Information on the status of the mother and child will be forwarded to GSK.
- Generally, follow-up will be no longer than 6 to 8 weeks following the estimated delivery date. Any termination of the pregnancy will be reported regardless of fetal status (presence or absence of anomalies) or indication for procedure.

[figure not shown]
Female participants who become pregnant

- Investigator will collect pregnancy information on any female participant, who becomes pregnant while participating in this study.
- The initial information will be recorded on the appropriate form and submitted to GSK within 24 hours of learning of a participant's pregnancy.
- Participant will be followed to determine the outcome of the pregnancy. The investigator will collect follow up information on participant and neonate, which will be forwarded to GSK. Generally, follow-up will not be required for longer than 6 to 8 weeks beyond the estimated delivery date.
- Any termination of pregnancy will be reported, regardless of fetal status (presence or absence of anomalies) or indication for procedure.
- While pregnancy itself is not considered to be an AE or SAE, any pregnancy complication or elective termination of a pregnancy for medical reasons will be reported as an AE or SAE.
- A spontaneous abortion (occurring at <22 weeks gestational age) or still birth (occurring at >22 weeks gestational age) is always considered to be an SAE and will be reported as such.
- Any SAE occurring as a result of a post-study pregnancy which is considered reasonably related to the study intervention by the investigator, will be reported to GSK as described in [Appendix 3](#). While the investigator is not obligated to actively seek this information in former study participants, he or she may learn of an SAE through spontaneous reporting.

Any female participant who becomes pregnant while participating will discontinue study intervention.

Note: The collection of pregnancy information will also apply to participants who continue to receive study intervention after the DCO date until last visit.

CCI

10.6. Appendix 6: Liver Safety: Required Actions and Follow-up Assessments

Phase I/II liver chemistry stopping and increased monitoring criteria have been designed to assure participant safety and evaluate liver event etiology (in alignment with the FDA premarketing clinical liver safety guidance).

<http://www.fda.gov/downloads/Drugs/GuidanceComplianceRegulatoryInformation/Guidances/UCM174090.pdf>.

Phase I/II Liver Chemistry Stopping Criteria and Required Follow up Assessments

Liver Chemistry Stopping Criteria – Liver Stopping Event Including participants with documented liver metastases/tumor infiltration at baseline AND entry criteria ALT >2.5 x ULN but ≤5 x ULN	
ALT-absolute	Both ALT ≥5 x ULN and ≥2 x baseline value
ALT Increase	Both ALT ≥3 x ULN and ≥1.5 x baseline value that persists for ≥4 weeks
Bilirubin^{1,2}	ALT ≥3 x ULN and bilirubin ≥2 x ULN (>35% direct bilirubin)
INR²	ALT ≥3 x ULN and INR >1.5, if INR measured
Cannot Monitor	Both ALT ≥3 x ULN and ≥1.5 x baseline value that cannot be monitored for 4 weeks
Symptomatic³	Both ALT ≥3 x ULN and ≥1.5 x baseline value associated with symptoms (new or worsening) believed to be related to liver injury or hypersensitivity
Required Actions and Follow up Assessments following ANY Liver Stopping Event	
Actions	

 • Immediately discontinue study treatment • Report the event to GSK within 24 hours • Complete the CRF within one week of occurrence and complete an SAE data collection tool if the event also meets the criteria for an SAE² • Perform liver event follow up assessments • Monitor the participant until liver chemistries resolve, stabilize, or return to within baseline (see MONITORING below) • Do not restart/rechallenge participant • If restart/rechallenge not allowed per protocol or not granted, permanently 	
 • Viral hepatitis serology⁴ • Obtain INR and recheck with each liver chemistry assessment until the transaminases values show downward trend. • Only in those with underlying chronic hepatitis B at study entry (identified by positive hepatitis B surface antigen) quantitative hepatitis B DNA and hepatitis delta antibody⁵. • Blood sample for pharmacokinetic (PK) analysis, obtained approximately 48hrs after last dose⁶ • Serum creatine phosphokinase (CPK) and lactate dehydrogenase (LDH). • Fractionate bilirubin, if total bilirubin ≥2xULN


discontinue study treatment and may continue as a participant in the study for any protocol specified follow up assessments
 
MONITORING:
 
For bilirubin or INR criteria:
 
 Repeat liver chemistries (include ALT, AST, alkaline phosphatase, bilirubin) and perform liver event follow up assessments within 24 hrs Monitor participants twice weekly until liver chemistries resolve, stabilize or return to within baseline A specialist or hepatology consultation is recommended 
For All other criteria:
 
 Repeat liver chemistries (include ALT, AST, alkaline phosphatase, bilirubin) and perform liver event follow up assessments within 24-72 hrs Monitor participants weekly until liver chemistries resolve, stabilize or return to within baseline 	
 Obtain complete blood count with differential to assess eosinophilia Record the appearance or worsening of clinical symptoms of liver injury, or hypersensitivity, on the AE report form Record use of concomitant medications on the concomitant medications report form including acetaminophen, herbal remedies, other over the counter medications Record alcohol use in the SAE form if reported as an SAE 
For bilirubin or INR criteria:
 
 Anti-nuclear antibody, anti-smooth muscle antibody, Type 1 anti-liver kidney microsomal antibodies, and quantitative total immunoglobulin G (IgG or gamma globulins). Serum acetaminophen adduct HPLC assay (quantifies potential acetaminophen contribution to liver injury in participants with definite or likely acetaminophen use in the preceding week [James, 2009]. NOTE: not required in China Liver imaging (ultrasound, magnetic resonance, or computerized tomography) and /or liver biopsy to evaluate liver disease.
--	---

1. Serum bilirubin fractionation should be performed if testing is available. If serum bilirubin fractionation is not immediately available, discontinue study treatment for that participant if $ALT \geq 3 \times ULN$ **and** bilirubin $\geq 2 \times ULN$. Additionally, if serum bilirubin fractionation testing is unavailable, **record presence of detectable urinary bilirubin on dipstick**, indicating direct bilirubin elevations and suggesting liver injury.
2. All events of $ALT \geq 3 \times ULN$ **and** bilirubin $\geq 2 \times ULN$ ($>35\%$ direct bilirubin) or $ALT \geq 3 \times ULN$ **and** INR >1.5 , if INR measured which may indicate severe liver injury (possible 'Hys Law'), **must be reported as an SAE (excluding studies of hepatic impairment or cirrhosis)**; INR measurement is not required and the threshold value stated will not apply to participants receiving anticoagulants
3. New or worsening symptoms believed to be related to liver injury (such as fatigue, nausea, vomiting, right upper quadrant pain or tenderness, or jaundice) or believed to be related to hypersensitivity (such as fever, rash or eosinophilia)
4. Includes: Hepatitis A IgM antibody; Hepatitis B surface antigen and Hepatitis B Core Antibody (IgM); Hepatitis C RNA; Cytomegalovirus IgM antibody; Epstein-Barr viral capsid antigen IgM antibody (or if unavailable, obtain heterophile antibody or monospot testing); Hepatitis E IgM antibody
5. PK sample may not be required for participants known to be receiving placebo or non-GSK comparator treatments. Record the date/time of the PK blood sample draw and the date/time of the last dose of study treatment prior to blood sample draw on the CRF. If the date or time of the last dose is unclear, provide the participant's best approximation. If the date/time of the last dose cannot be approximated OR a PK sample cannot be collected in the time period indicated above, do not obtain a PK sample. Instructions for sample handling and shipping are in the SRM.

Phase I/II Oncology Liver Chemistry Increased Monitoring Criteria With Continued Therapy

Liver Chemistry Increased Monitoring Criteria – Liver Monitoring Event	
Criteria	Actions

Participant with entry criteria ALT $\leq 2.5 \times$ ULN
 
ALT $\geq 3 \times$ ULN but $< 5 \times$ ULN and bilirubin $< 2 \times$ ULN, without symptoms believed to be related to liver injury or hypersensitivity and who can be monitored weekly for 4 weeks
 
Participant with documented liver metastases/tumor infiltration at baseline AND entry criteria ALT $> 2.5 \times$ ULN but $\leq 5 \times$ ULN
 
ALT $\geq 3 \times$ ULN and 1.5 x baseline value but ALT $< 5 \times$ ULN and 2 x baseline value and bilirubin $< 2 \times$ ULN, without symptoms believed to be related to liver injury, or hypersensitivity and who can be monitored weekly for 4 weeks
	
 Notify the GSK medical monitor within 24 hours of learning of the abnormality to discuss participant safety. Participant must return weekly for repeat liver chemistries (ALT, AST, alkaline phosphatase, bilirubin) until they resolve, stabilize or return to within baseline If at any time participant meets the liver chemistry stopping criteria, proceed as described above 
For participants with entry criteria ALT $\leq 2.5 \times$ ULN
 
 If, after 4 weeks of monitoring, ALT $< 3 \times$ ULN and bilirubin $< 2 \times$ ULN, monitor participants twice monthly until liver chemistries normalize or return to within baseline. 
For participants with documented liver metastases/tumor infiltration at baseline AND entry criteria ALT $> 2.5 \times$ ULN but $\leq 5 \times$ ULN
 
 If, after 4 weeks of monitoring, ALT $< 3 \times$ ULN and $< 1.5 \times$ baseline value, and bilirubin $< 2 \times$ ULN, monitor participants twice monthly until liver chemistries normalize or return to within baseline

Reference:

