Hematology and hemostaseology	X	X	X	X	X	X	X	X	Q4W	X	X		Details on blood tests under this category is listed in Table 6 . At visits where blood tests are required, results should be reviewed prior to dosing. Hematology should be repeated if not performed within 24 hours of D1.	
Clinical chemistry	X	X	X	X	X	X		X	Q4W	X	X		Clinical chemistries are listed in Table 6 . At visits where blood tests are required, results should be reviewed prior to dosing. Chemistry should be repeated if not performed within 24 hours of D1.	
Free T ₄ and TSH	X			X			X	Q6W		X			See Appendix 2	
Urinalysis	X	As clinically indicated											See Appendix 2	
AE review	See notes							X	X	X			Start at Consent. See Section 8.5.1 . The 12-week Safety Follow-up and Long-term Follow-up may be conducted via telephone calls or patient chart reviews as necessary unless there is medical necessity requiring a clinical visit. All nonserious related AEs and AEs of interest will be followed until the event is resolved, stabilized, otherwise explained, or the participant is lost to follow-up (as defined in Section 7.3) All other AEs will be followed until the last follow up visit.	

	Screening	Intervention (treatment) Period								Safety Follow-up		Long Term Follow-up	Notes	
Assessment and Procedures	45 Day- to first dose	V1	V2	V3	V4	V5	V6	V7	Until PD	EOT	28 Days (±5 Days) After Last Treatment	12 Weeks (± 2 Weeks) After Last Treatment	Every 12 Weeks (± 2 Weeks)	D1: All assessments must be performed on day indicated (unless noted in assessment "Notes"). Day 15 through PD: Visits can be performed ±3 days. EOT: On day of or within 7 days of decision to discontinue. Follow up: Visits can be performed ±2 Weeks.
		W1	W3	W5	W7	W9	W11	W13						
		D1	D15	D29	D43	D57	D71	D85						
SAE review	See notes							X	X	X	X	X	Start at Consent. For ongoing SAEs see Section 8.5.1. The 12-week Safety Follow-up and Long-term Follow-up may be conducted via telephone calls or patient chart reviews as necessary unless there is medical necessity requiring a clinical visit. All SAEs, will be followed until the event is resolved, stabilized, otherwise explained, or the participant is lost to follow-up (as defined in Section 7.3).	
Concomitant medication review	X	X	ongoing				X	X	X	X	X	X		
Study Intervention and Pretreatment														

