Abbreviations: ANC = Absolute neutrophil count; ALT = alanine aminotransferase; CrCl = creatinine clearance; ECHO=echocardiogram; eGFR=estimated glomerular filtration rate; MUGA= multigated acquisition scan; ULN = upper limit of normal; WNL = within normal limits

- a. Participants may be transfused or receive growth factor treatment to meet minimum hematologic values up to 10 days prior to determining eligibility.
- b. Participants receiving anticoagulant therapy exempt.
- c. Estimated CrCl/eGFR is required to be calculated using the Chronic Kidney Disease Epidemiology Collaboration (CKD-EPI) or Cockcroft-Gault formula; either formula is acceptable and must be consistently used for each participant throughout the study. Alternatively, investigators may use 24-hour urine to determine CrCl (refer to [Appendix 11](#)).
- d. MUGA is acceptable if ECHO is not available; for each participant the same modality must be used for all subsequent evaluations.

8. Life expectancy of at least 12 weeks.
9. A female is eligible if she is not pregnant or breastfeeding, and at least one of the following conditions applies:
 - Not a woman of childbearing potential (WOCBP) as defined in [Appendix 4](#).

OR

- If a WOCBP, use a highly effective contraceptive method (i.e., with a failure rate of $<1\%$ per year), preferably with low user dependency, as described in [Appendix 4](#) for the following time periods:
 - Before the first dose of the study intervention(s), if using hormonal contraception:
 - Has completed at least one 4-week cycle of an oral contraception pill and either had or has begun her menses.

OR

- Has used a depot contraceptive or extended-cycle oral contraceptive for least 28 days and has a documented negative pregnancy test using a highly sensitive assay.

- During the intervention period
- After the study intervention period (i.e., after the last dose of study intervention is administered) for at least 2 months.

The investigator evaluates the effectiveness of the contraceptive method in relationship to the first dose of study intervention.

Has a negative serum or highly sensitive urine pregnancy test, as required by local regulations, within 24 hours before the first dose of study intervention. If a urine test cannot be confirmed as negative (e.g., an ambiguous result), a serum pregnancy test is required.

Additional requirements for pregnancy testing during and after study intervention are in [Appendix 2](#).

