7.1.2. Liver Chemistry Stopping Criteria

Liver chemistry stopping, and increased monitoring criteria have been designed to assure participant safety and evaluate liver event etiology.

Discontinuation of study intervention for abnormal liver tests is required when:

- a participant meets one of the conditions outlined in [Appendix 6](#).
- when in the presence of abnormal liver chemistries not meeting protocol-specified stopping rules, the investigator believes study intervention discontinuation is in the best interest of the participant.

Figure 2 Phase I/II Liver Chemistry Stopping and Increased Monitoring Algorithm including Participants WITH documented liver metastases/tumor infiltration at baseline AND entry criteria ALT >2.5x ULN but \leq 5x ULN

Liver Safety Required Actions and Follow up Assessments Section can be found in [Appendix 6](#).

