Routine Urinalysis ³	
 • Specific gravity, physical appearance, color • pH, glucose, protein, blood, ketones, bilirubin, urobilinogen, nitrite, leukocyte esterase, by dipstick • Microscopic examination (if blood or protein is abnormal) 		
Thyroid Panel	
 • Free T₄, TSH 		

Laboratory Assessments ¹	Parameters All parameters are performed locally
Other Screening Tests	
 • Follicle-stimulating hormone and estradiol (as needed in women of non-childbearing potential only) • Highly sensitive serum or urine human chorionic gonadotropin (hCG) pregnancy test (as needed for women of childbearing potential)⁴ • Hepatitis B surface antigen [HBsAg], and hepatitis C virus antibody. • TST, QuantiFERON-TB-Gold, or T-SPOT (if positive history of tuberculosis exposure)⁶ 
The results of each test must be entered into the CRF.

NOTES : ALT = alanine aminotransferase; ANC = absolute neutrophil count; aPTT = activated partial thromboplastin time; AST = aspartate aminotransferase; β -hCG = beta-human chorionic gonadotropin; BUN = blood urea nitrogen; CRP = C reactive protein; GGT = gamma-glutamyltransferase; HBV = hepatitis B virus; HCV = hepatitis C virus; INR = international normalized ratio; MCH = mean corpuscular hemoglobin; MCHC = mean corpuscular hemoglobin concentration; MCV = mean corpuscular volume; RBC = red blood cell; RDW = red cell distribution width; T4 = free thyroxine; TSH = thyroid-stimulating hormone; TST = tuberculin skin test; WBC = white blood cell.

1. Performed as indicated in Section 1.3 (Schedule of Activities).
2. Details of liver chemistry stopping criteria and required actions and follow-up assessments after liver stopping or monitoring event are given in Section 7.1.2 and Section 10.6. All events of $ALT \geq 3 \times$ upper limit of normal (ULN) and bilirubin $\geq 2 \times$ ULN ($> 35\%$ direct bilirubin) or $ALT \geq 3 \times$ ULN and international normalized ratio (INR) > 1.5 , if INR measured, which may indicate severe liver injury (possible Hy's Law), must be reported as an SAE (excluding studies of hepatic impairment or cirrhosis).
3. Routine urinalysis performed at Screening and as clinically indicated thereafter.
4. Local urine or serum pregnancy testing, as required by local regulation or IRB/IEC.
5. Chemistry and Hematology should be repeated if not performed within 24 hours of Day 1.

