2.2 Hepatitis (management based on guidelines by Brahmer et al., 2018, with modifications)	

Definition: A disorder characterized by a viral pathologic process involving the liver parenchyma
 
Diagnostic work-up
 
Monitor patient for abnormal liver blood tests: AST, ALT, and bilirubin prior to each infusion and/or weekly if G1 liver function test elevations. No treatment is recommended for G1 liver function test abnormality
 
For G2 or higher:
 
Work-up for other causes of elevated liver enzymes should be tested, viral hepatitis, alcohol history, iron study, thromboembolic event, liver ultrasound, cross-sectional imaging for potential liver metastasis from primary malignancy. If suspicion for primary autoimmune hepatitis is high, can consider ANAs, antismooth muscle antibodies, antineutrophil cytoplasmic antibodies. If patients with elevated alkaline phosphatase alone, g-glutamyl transferase should be tested. For isolated elevation of transaminases, consider checking CK for other etiologies
	
Grading	Management
All patients	
Counsel all patients to be aware of and inform their health care provider immediately if they experience:
 
Yellowing of skin or whites of the eyes
 
Severe nausea or vomiting
 
Pain on the right side of the abdomen
 
Drowsiness
 
Dark urine (tea colored)
 
Bleeding or bruising more easily than normal
 
Feeling less hungry than usual

G1: Asymptomatic (AST or ALT > ULN to 3.0 x ULN and/or total bilirubin > ULN to 1.5 x ULN)	
Continue ICPi with close monitoring; consider alternate etiologies
 
Monitor laboratories one to two times weekly
 
Manage with supportive care for symptom control

G2: Asymptomatic (AST or ALT >3.0 to \leq 5 x ULN and/or total bilirubin >1.5 to \leq 3 x ULN). For participants with metastatic disease to liver and elevated transaminases at baseline, see Appendix 6 for grading that accommodates baseline liver chemistry values.	
Permanently discontinue ICPi if:
 
 - ALT \geq3 x ULN persists for \geq4 weeks - ALT \geq3 x ULN and bilirubin \geq2 x ULN ($>35\%$ direct bilirubin) - ALT \geq3 x ULN and INR >1.5, if INR measured

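### The liver rule (ALT ≥3 x ULN with INR >1.5) exempts anticoagulated participants in Appendix 6 but not in Table 6 or Table A2, so one participant can get conflicting treatment and SAE outcomes

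*Protocol*

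**What the plan says.** Section 7.1.2 requires treatment to stop when "a participant meets one of the conditions outlined in" Appendix 6. One of those conditions is "ALT ≥3 x ULN and INR >1.5, if INR measured". Note 2 is attached to that criterion, to the bilirubin criterion and to the action on completing an SAE form. It ends: "INR measurement is not required and the threshold value stated will not apply to participants receiving anticoagulants". When no stopping criterion is met, Appendix 6 has a second table, headed "Phase I/II Oncology Liver Chemistry Increased Monitoring Criteria With Continued Therapy".

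Two other places repeat the INR rule without the exemption:

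- **Section 10.2, Table 6, note 2** covers all events of ALT ≥3 x ULN with either raised bilirubin or INR >1.5: "if INR measured, which may indicate severe liver injury (possible Hy's Law), must be reported as an SAE".
- **Section 10.9, Table A2, item 2.2 Hepatitis, Grade 2** lists, among the grounds for permanently stopping treatment, ALT ≥3 "x ULN and INR >1.5, if INR measured".

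Two further provisions show that the case can occur. Section 5.1, criterion 7, footnote b, on the INR or PT entry limit, says "Participants receiving anticoagulant therapy exempt". Table 1 schedules "Hematology and hemostaseology" at screening, through the treatment visits and every 4 weeks thereafter, and the Table 6 hematology panel includes INR.

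**The concern.** A site facing a raised ALT in an anticoagulated participant has three texts to consult, and they do not agree. Whether treatment continues, is held or stops for good, and whether an SAE is filed, depends on which text is followed.

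The proviso that INR has been measured does not limit the rule while the schedule in Table 1 applies, because INR is then a protocol test. Participants can be on anticoagulants at entry. They can also start during the study: Table A9 allows treatment to continue after a Grade 2 venous thrombosis and accepts oral anticoagulants for the long term.

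At stake are the treatment of individual participants and the consistency of two safety summaries. SAP Sections 14.1 and 14.1.2 tabulate serious TEAEs and TEAEs leading to permanent discontinuation. If sites follow different texts, those counts mix two definitions.

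**Working it through.** The plan gives no figure to reproduce. The check applies each text to one case, then works out the range in which the baseline condition matters.

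**Assumed case.** On an anticoagulant; INR 2.4; entry ALT 1 x ULN; ALT now 3.5 x ULN, raised for less than 4 weeks; bilirubin normal; no symptoms; weekly monitoring feasible.

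**Appendix 6, criterion by criterion**

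- ALT absolute (≥5 x ULN and ≥2 x baseline): 3.5 < 5, not met.
- ALT increase (≥3 x ULN and ≥1.5 x baseline for ≥4 weeks): duration not reached, not met.
- Bilirubin ≥2 x ULN: not met.
- INR >1.5: 2.4 > 1.5, but note 2 removes the threshold.
- Cannot be monitored: not met.
- Symptomatic: not met.
- Monitoring event (ALT ≥3 and <5 x ULN, bilirubin <2 x ULN, no symptoms, weekly checks possible): met.

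**The texts side by side**

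| Text | Treatment | SAE under the INR rule |
|---|---|---|
| Appendix 6 with note 2 | Continues, with increased monitoring | No |
| Table 6 note 2 | Not addressed | Yes |
| Table A2, Grade 2, as written | Permanently stopped | Not addressed |
| Table A2, Grade 2, exemption read in | Held temporarily | Not addressed |

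The result is the same for any entry ALT ≤2.5 x ULN, ALT above 3 and below 5 x ULN and INR >1.5, provided the other Appendix 6 stopping criteria are not met. At ALT ≥5 x ULN and ≥2 x baseline, Appendix 6 stops treatment anyway and only the SAE conflict remains.

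The last row shows a further difference that does not depend on anticoagulants. When none of its permanent-stop criteria is met, Table A2 holds treatment, while Appendix 6 continues it.

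**Baseline condition.** For the persistence and cannot-monitor criteria, Appendix 6 requires ALT ≥3 x ULN and ≥1.5 x baseline; Table A2 requires only ALT ≥3 x ULN. With entry ALT b (in x ULN), the texts differ where 3 ≤ ALT < 1.5b, which needs 1.5b > 3, so b > 2.0.

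- b = 2.0: 1.5 × 2.0 = 3.0, no gap.
- b = 2.25: 1.5 × 2.25 = 3.375, gap from 3 to 3.375.
- b = 2.5 (the entry limit without liver metastases): 1.5 × 2.5 = 3.75, gap from 3 to 3.75.

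**Size in the summaries.** One participant of 25 is 1/25 = 4%.

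**The case against.** The strongest reply is that Appendix 6 governs. Section 7.1.2 makes it the place where mandatory liver discontinuation is defined. Table 6 note 2 opens by referring to Sections 7.1.2 and 10.6 and reads like a shortened copy of the Appendix 6 note. Table A2 also points to Appendix 6.

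This softens the conflict but does not remove it. The Table 6 pointer concerns stopping criteria, actions and follow-up; its SAE sentence follows separately, covers all events and has no exception. In Table A2 one pointer concerns grading for participants with liver metastases and raised baseline transaminases. The other comes in the branch reached once the permanent-stop criteria have been judged absent. Section 6.8.1 sends immune-related events to Appendix 9. The clause in Section 7.1.4 giving precedence to the Section 6.8 guidance concerns only the general adverse drug reaction rules that follow it. No text ranks Appendix 6 against Table A2.

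The following limits do stand:

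- Table A2 offers recommendations for immune-related hepatitis. It does not cover every liver chemistry event, so its permanent stop cannot be read as applying to all participants.
- A reader might take Section 7.1.2.1 to make the stop irreversible. That section bars restart after the liver stopping criteria are met, and the example participant meets none in Appendix 6. Permanence here comes only from Table A2.
- Appendix 6 requires the medical monitor to be told of a monitoring event within 24 hours, so such a case would probably be discussed.
- Enrolment has ceased and 25 participants have been treated. The documents do not say how many took anticoagulants or had ALT ≥3 x ULN.

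**Conclusion.** The contradiction is real. Followed as written, the protocol gives the same anticoagulated participant different treatment and SAE-reporting outcomes in Appendix 6, Table 6 and Table A2. The missing baseline condition is a smaller second conflict. Without liver metastases it arises only for entry ALT above 2.0 and up to 2.5 x ULN, and for ALT below 3.75 x ULN at most.

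The effect on reported results is limited. The 4 points per participant is a ceiling: the SAP counts participants, so someone with another serious TEAE, or another TEAE that led to discontinuation, adds nothing. These counts support the secondary endpoint, frequency and severity of AEs; they are not the endpoint as named. The ORR calculation does not use them. Events after the data cut-off do not enter the clinical database. The treatment and SAE conflict nevertheless remains for anyone still on treatment, since Section 6.10 ties continued access to the discontinuation criteria and Section 8.5.2 keeps SAE reporting open. INR testing then follows local practice.

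A reader might also infer that the exemption is the correct rule, or that the SAE report would be false. The documents do not settle either question, and this review takes no position on it.

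**What to change.** Reconcile Table 6 note 2, the Appendix 6 stopping and monitoring tables with their notes, and the Grade 2 entry of Table A2 item 2.2, so that a single set of liver stopping, holding and SAE-reporting criteria applies. The reconciled text needs to settle four things:

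- whether the INR threshold applies to participants on anticoagulants, for stopping and for SAE reporting;
- whether the 1.5 x baseline condition applies to the persistence and cannot-monitor criteria;
- whether treatment is held or continued when no permanent-stop criterion is met;
- which text prevails when a liver event is managed as immune-related hepatitis.

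The sponsor's clinical team decides each of these. The cost is protocol wording or a clarification letter to sites, with no new data, visits or participants.
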